In summary, routine data collection on health and social care needs and patterns of service access by the NPS is currently limited. If we are to improve the health and wellbeing of this deprived population, it is crucial that we improve assessment processes to provide an accurate picture of their needs, and patterns of service access. This is essential to inform probation practice, and enable evidence-based commissioning of services. We also need to develop QIs to enable us to examine the extent to which needs are being met, and whether appropriate processes are in place to support this. Doing these things would benefit patients through improved health and reduced health-inequalities, and would produce a 'community dividend' including a reduction in offending and avoidable use of crisis care. This would produce cost savings for the NHS.

STUDY OBJECTIVES AND PURPOSE

PURPOSE

This project aims to support evidence-based commissioning of appropriate and accessible services for people on probation. We wish to improve data collection within probation around the health and social care needs of people on their caseload and the extent to which they are being met by current service provision; and to develop quality indicators for the quality of health and social care that this population receive.

PRIMARY OBJECTIVE

Improve the measurement, understanding and recording of the health and social care needs of people on probation, and their patterns and experiences of service access (better data collection)

SECONDARY OBJECTIVE(S)

Develop quality indicators for the quality of the healthcare that people on probation receive

OUTCOME MEASURES/ENDPOINTS

PRIMARY OUTCOME MEASURE/ENDPOINT

Overview of health and social care needs and the extent to which they are being met by current service provision

Creation of quality indicators

STUDY DESIGN

This is a multi-centre, multi-methods study involving:

Page 12 of 25

- Surveys of the health and social care needs of people in contact with probation in four probation Local Delivery
 Units (improving data collection) and telephone/online interviews to gather feedback around the administration of
 these
- 2) Development of quality indicators using the modified Rand method detailed by Van Engen-Verheul et al., (2011) [28], which includes the following:

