- a. A systematic review of the literature to identify existing quality indicators for health and social care in use in probation outside of England, or elsewhere in the criminal justice system
- b. A service user panel focus group with individuals with lived experience of the criminal justice system to support the development of quality indicators
- c. Two online surveys with an expert panel of people working in the health and justice field. The first of these will ask participants what they think the characteristics of excellent health and social care for people on probation are, and how this could be measured (i.e. what they think good quality indicators would look like). The second survey will ask participants to rate a draft list of quality indicators compiled based on the findings from the systematic review, service user, and expert panels. The expert panel will be asked to rate these quality indicators on a 5-point Likert scale based on whether or not they have a clear link to outcomes for service users, can be a departure point for improvement actions, and are practical to implement. A mean score will be derived for each indicator. Participants will also be able to suggest additional indicators if they feel that something is missing
- d. Finally, the expert panel will discuss the final list of quality indicators developed from the study to enable any final amendments to be made if needed.

DATA ANALYSIS

Surveys of health and social care needs and the extent to which they are being met by current service provision: data will be entered into a database by a Research Assistant for analysis by the Medical Statistician. Analysis is anticipated to take place in SPSS and STATA. Demographic data will be used to determine the extent to which survey respondents reflect the population within the national probation caseload. The survey data will be weighted to better represent the national population in terms of its demographic profile using an appropriate weighting methodology propensity score weighting. Data will be analysed using descriptive statistics to show a) the prevalence of needs, and b) patterns of service access and the extent to which needs are being met. Mixed effects models (also known as multilevel models) will be used to predict health and social care needs based on service user and area characteristics.

Systematic review: Existing quality indicators will be extracted from the included papers for inclusion in the online surveys.

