Service user panel focus group: Participants will be interviewed using a semi-structured interview guide co-designed by the Peer Researchers. The focus group will be conducted online and recorded, transcribed verbatim, and analysed by the research team in NVivo using thematic analysis with support from the Peer Researchers.

Online surveys for development of quality indicators: Data from the first survey will be entered into NVivo (qualitative data analysis software) and analysed using thematic analysis. Ratings from the second survey will be extracted into a database for analysis. This will simply involve calculating the mean score for each indicator.

Draft analyses will be presented at project steering groups, with additional work, or revisions being undertaken if needed following discussion at these meetings.

Notes will be taken in Word during the discussion of the final draft indicators, and used to inform any final changes to them.

STUDY SETTING

Surveys of health and social care needs and the extent to which they are being met by current service provision: Data will be collected across four probation Local Delivery Units containing a mixture of urban and rural areas. Feedback will be collected from probation staff via online/telephone interviews.

Systematic review: Will be conducted at the University of Lincoln.

Service user panel focus group: Participants will recruited by Revolving Doors Agency peer researchers, and the focus group will take place online or at a location selected by Revolving Doors Agency.

Page 13 of 25

Online surveys for development of quality indicators (expert panel): These will take place online, with the final discussion taking place via (online) teleconference.

SELECTION OF PARTICIPANTS

ELIGIBILITY CRITERIA

Inclusion Criteria

Surveys of health and social care needs and the extent to which they are being met by current service provision: Any individual aged 18+ years that is on probation, in the community (including probation Approved Premises) in one of the Local Delivery Units selected for the study that probation staff believe has sufficient understanding of English to complete the survey, and capacity to provide informed consent

Online/telephone interviews: staff that have administered the surveys of health and social care needs.

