All individuals in these areas will be invited to participate in the survey when they attend at probation premises, or by remote contact (telephone or online) if they attend less than once a month, or are not able to attend due to ongoing restrictions in relation to covid-19 - i.e. probation staff are not selecting participants, they are giving details of the study to all potential participants on the caseload.

An email will be sent via our probation co-applicant to all staff that may have played a role in administering the survey to ask for volunteers to participate in an online/telephone interview to provide feedback on what this was like.

DEVELOPING QUALITY INDICATORS

Page 14 of 25

The service user panel will be recruited by Revolving Doors staff and their Lived Experience Peer Researchers from those involved in their Lived Experience research.

The expert panel will be recruited by the Research Team. A National Probation Service Divisional Director is part of this team, and will invite National Probation Service Health Leads to participate if they wish to. The research team already have a list of potential participants based in the other key organisations listed earlier in this form that they can invite to participate based on their appropriateness due to their roles within the health and justice arena. The study has already been discussed with members of some of these organisations, who have been supportive of the research proposed.

Size of sample

We anticipate that there will be 3000-4000 people on probation across the Local Delivery Units, all of whom will be invited to complete a survey. We anticipate that we will achieve a minimum return rate of 10% but will aim to achieve a higher rate (likely to be between 33% and 50%). This should give sufficient data to be able to complete the analysis set out above. We would like 5-10 staff to take part in online/telephone interviews to provide feedback on this.

We aim to recruit 5-10 people with lived experience of the criminal justice system for the focus group, and 10-15 people in appropriate roles in the health and justice field for the expert panel. This should be a manageable number of individuals and give us sufficient data to gain insight into service user views and experiences, and to ensure that a range of appropriate organisations are represented on the expert panel.

Sampling technique

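### A mean alone cannot show whether the expert panel agreed on an indicator or found it weak on one of the three rating criteria

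*Protocol*

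**What the plan says.** Under Study Design, item 2, the protocol describes "Development of quality indicators using the modified Rand method". Item 2c gives the panel's task in survey two as follows: "rate these quality indicators on a 5-point Likert scale based on whether or not they have a clear link to outcomes for service users". It adds two further properties, namely whether the indicators "can be a departure point for improvement actions, and are practical to implement". Study Regimen repeats these three properties. Neither place says whether each property gets its own rating or one rating covers all three.

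The analysis is given three times. Study Design 2c says "A mean score will be derived for each indicator". The Study Summary and the Data Analysis section both say of the second-survey ratings: "This will simply involve calculating the mean score for each indicator". No spread, agreement measure or result by criterion is mentioned.

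Size of sample plans for "10-15 people in appropriate roles in the health and justice field for the expert panel", chosen so that several organisations are represented.

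Two steps follow. Draft analyses go to the steering group, which may ask for more work. Then, under Study Design 2d, "the expert panel will discuss the final list of quality indicators developed from the study to enable any final amendments to be made". Of that meeting the Data Analysis section says: "Notes will be taken in Word during the discussion of the final draft indicators". Schedule of Procedures puts survey two in months 11-12 and the discussion in month 16; the Study Summary allows one hour for it.

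**The concern.** The word "simply" in the Data Analysis section makes the mean the whole quantitative treatment of the ratings. This is a stated choice, not a detail left open for an analysis plan.

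The choice suits the task poorly. The raters come from commissioning, probation, the inspectorate and the ministry, and practicality in particular may look different from each of those positions, so split ratings are foreseeable. The three properties are also distinct: an indicator can be closely linked to outcomes and still be hard to implement. A single mean discards both kinds of information.

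Creation of quality indicators is listed under the primary outcome heading, although it is the secondary objective. The final set is to be given to the National Probation Service and disseminated further. Users of the set will want to know whether the panel agreed on each indicator and whether it was judged workable. The stated analysis can answer neither question.

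**Working it through.** The protocol gives no sample-size, precision or cut-off figure for the rating exercise, so there is no figure of its own to reproduce. The check asks what a mean can and cannot distinguish.

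**Inputs.** Scale 1 to 5, three properties (Study Design 2c); 10 to 15 raters (Size of sample). The rating patterns below are hypothetical.

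**1. Agreement against disagreement, same mean.**

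| Raters | Ratings | Mean | SD | Median | At 4-5 | At 1-2 |
|---|---|---|---|---|---|---|
| 10 | ten 4s | 40/10 = 4.0 | 0 | 4 | 10 | 0 |
| 10 | seven 5s, two 2s, one 1 | (35+4+1)/10 = 4.0 | 1.63 | 5 | 7 | 3 |
| 15 | fifteen 4s | 60/15 = 4.0 | 0 | 4 | 15 | 0 |
| 15 | eleven 5s, one 2, three 1s | (55+2+3)/15 = 4.0 | 1.73 | 5 | 11 | 4 |
| 10 | ten 3s | 30/10 = 3.0 | 0 | 3 | 0 | 10 - 10 = 0 |
| 10 | five 5s, five 1s | (25+5)/10 = 3.0 | 2.11 | 3 | 5 | 5 |

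The last pair ties on the median as well as the mean, so the median alone would not be enough; the percentages at each end are what separate it.

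**2. How much dissent a mean of 4.0 can hold.** Suppose k of n raters score 2 and the rest score 5. The mean is at least 4 when 5(n - k) + 2k ≥ 4n, that is k ≤ n/3: up to 3 of 10, or 5 of 15. If the dissenters score 1, the condition is 5(n - k) + k ≥ 4n, that is k ≤ n/4: up to 2 of 10, or 3 of 15.

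**3. Weakness on one property.**
- If rated separately and averaged: (5+5+2)/3 = 4.0, the same as (4+4+4)/3; (5+5+1)/3 = 3.67, the same as (4+4+3)/3.
- If one rating covers all three: each rater does the weighing unseen, and no later analysis can recover the property-level view.

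**4. Do the later steps restore the information?** Steering-group review and the panel discussion could bring disagreement out informally. Neither is told to look at spread or at results by criterion, and the analysis they receive contains neither. The Withdrawal section says the expert surveys are anonymous, so low raters could not be approached individually for their reasons.

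**The case against.** The strongest defence is that the mean is only one input. The indicators also draw on a systematic review, a service user focus group, a thematic first survey, suggestions of missing indicators, steering-group review and a discussion by the same panel. That stands, and it limits the consequence: the mean is not the whole development process. It does not answer the point, because nothing ties those steps to disagreement or to a weak criterion.

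Four stronger readings are tempting, and the documents do not support them.

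- *That indicators will be ranked, kept or dropped on the mean.* The protocol says only that a mean is derived.
- *That each of the three properties is a must-pass requirement, or that criterion scores are averaged.* The properties are joined by "and", but no pass rule is stated, and the rating format is left open. The loss of information occurs under either format.
- *That the absence of a retention rule is itself an error.* Such a rule may sit in an analysis plan or in the cited method paper, neither of which is at hand. The protocol text also does not claim a consensus-based set.
- *That with 10-15 raters, ordering by means is mostly noise.* No rating SD is given. Using t(0.975, n-1) × SD/√n with assumed SDs of 0.5, 1.0 and 1.5, the 95% half-width is 0.36, 0.72 and 1.07 at n = 10, and 0.28, 0.55 and 0.83 at n = 15. Whether that matters depends on the spread between indicators, which is unknown. The same purposively chosen panel also rates every indicator, so these intervals have doubtful meaning.

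**Conclusion.** The point holds as a cheap improvement to a stated method. An indicator with a mean of 4.0 may have the whole panel's support, or may be scored 2 by up to a third of it; it may be sound on all three properties, or score 2 on one of them. The stated analysis reports these cases identically.

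The tie arithmetic needs no distributional assumption. How often such patterns will occur cannot be known beforehand; the expectation that they may occur rests on the mixed make-up of the panel. The weight is moderate: the exercise is descriptive and serves the secondary objective, though its product is listed as an outcome and will be disseminated.

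**What to change.** Amend Study Design 2c, the Study Summary and the Data Analysis section as follows.

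1. In survey two, collect a separate 5-point rating for each of the three criteria.
2. For each indicator and criterion, report the median and the percentages rating 4-5 and 1-2. Keep the mean beside them.
3. Take these results to the final panel discussion, with indicators flagged by a rule written before survey two opens. The categories must not overlap. For illustration, apply in this order to each criterion: *low* if fewer than 50% rate 4-5; otherwise *split* if at least 20% rate 1-2; otherwise *not flagged*. Here seven 5s, two 2s and a 1 (70% at 4-5, 30% at 1-2) is split, ten 3s is low, and ten 4s is not flagged. The percentages are examples and have no source in the protocol.

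**Cost.** No new participants; a few spreadsheet columns and one paragraph. If one combined rating was intended, the survey becomes longer, and the 25 minutes allowed for it in the Study Summary should be checked. The thresholds are a judgement and need to be owned as such.

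**Timing.** Spread can be computed afterwards from the exported ratings. Results by criterion cannot, if only a combined rating was collected, so the first step has to be settled before survey two opens.

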After consent is taken, the survey can then be either self-completed with a member of probation staff present, or completed by a member of probation staff on the participant's behalf, with the staff member reading through it with the participant either face-to-face or via remote contact (e.g. phone/Microsoft Teams). This is to ensure that the study is as inclusive as possible. The survey will only be administered remotely if the participant has an appropriate (private) space in which to take part, and individuals will not be able to self-complete the survey and return it via email, as probation staff need to review the answers straight after it is completed.

Probation staff will use their judgement to select who has sufficient understanding of English to take part, and capacity to provide informed consent. It will be made clear to potential participants that taking part is voluntary and individuals

Page 15 of 25

are free to withdraw at any time, without giving any reason, and without their legal rights or relationship with probation being affected. However, as participation is anonymous it will not be possible to withdraw data once submitted, as the research team will have no way of identifying individual participants.

If a member of probation staff completes the survey with a participant, they will already be aware of their answers. If the participant self-completes it at a face-to-face appointment, they will then hand it back to a member of probation staff, who will immediately review the answers to check if they indicate any increased risk of harm to self or others (e.g. feeling suicidal). In all cases, after the responses have been read by probation staff, they will then be placed in a pre-addressed freepost envelope for return to the research team.

Potential participants in online/telephone interviews for feedback around administration of the survey will receive an information sheet and consent form attached to an email sent to all relevant staff via probation.

Potential participants in the service user panel will be approached by Revolving Doors and given an information sheet and consent form to read and complete prior to participating. They will be recruited via their Peer Researcher/Lived Experience network.

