Potential participants in the expert panel will be approached by a member of the research team by telephone or email (publicly available or provided after a telephone conversation on their public number), and given an information sheet and consent form to read and complete prior to participating. They will be selected based on having an appropriate job at an organisation that is relevant for inclusion in the research.

Participant Payment

Participants will not be paid to participate in the study.

CONSENT

Informed consent will be provided for the surveys of health and social care needs. A written or typed signature (esignature/consent) will be provided on the consent form.

The recruiting Investigator (member of probation staff) will explain the details of the study and provide a Participant Information Sheet (and any other study related literature), ensuring that the participant has sufficient time to consider participating or not. Opportunity will be given to the participant to ask any questions they may have has concerning study participation. Every effort has been made to ensure appropriate readability for the information sheet, consent form and survey, which has been piloted with people with lived experience of the criminal justice system, but potential participants can also request assistance from probation staff to read and complete the forms if desired.

Individuals participating in the online/telephone interviews will provide written informed consent by returning the consent form to the member of probation staff inviting people to take part, who will then upload these to a shared file for the research team to see.

Similarly, potential members of the service user panel will provide written informed consent after receiving an information sheet and consent form from the research team about those elements of the study, either as a hard copy, or via an email from Revolving Doors Agency (wet ink signature/e-consent). In the case of the expert panel, the information sheet and consent form will be incorporated into the online survey, so consent will be provided as e-consent.

[figure not shown]
The process for obtaining participant informed consent for all elements of the research will be in accordance with the REC guidance, and Good Clinical Practice (GCP) and any other regulatory requirements that might be introduced.

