Our core focus is on recording past diagnoses, and using the CANSAS-P to identify areas of need, and if they have been met. We have also included the AUDIT-C, DAST-10 and CORE-10 as these provide additional information by indicating severity of need in key areas. This will inform probation practice (for example cut-off scores on the CORE-10 can be used to indicate a need for referral to primary [6+] or secondary care [10+]), and enable assessment of the relationship between level of need and whether or not the need has been met - providing useful data for service commissioners and providers.

Online/telephone interviews will be based on a semi-structured interview guide to ascertain feedback on what it was like to implement the survey and if/how this could be incorporated into routine practice.

DEVELOPING QUALITY INDICATORS

Individuals participating in the service user panel will be asked to complete a consent form, and to contribute to a focus group in which they will be asked to describe positive and negative experiences of accessing care, and discuss what they think probation should know about their health, what they think the characteristics of excellent care are, and how this could be measured. The focus group will either take place at an appropriate location selected by Revolving Doors or using Microsoft Teams.

Individuals participating in the expert panel will be asked to complete a consent form (provided online at the start of the surveys), and to complete two online surveys. The first survey will ask them what they think the characteristics of excellent health and social care for people on probation are, and how this could be measured (i.e. what they think good quality indicators would look like). The second survey will ask them to rate a draft set of quality indicators on a 5-point Likert scale based on whether or not they have a clear link to outcomes for service users, can be a departure point for improvement actions, and are practical to implement. They will also be asked to state if they feel that anything is missing. Finally, these individuals will participate in a discussion of the final quality indicators to inform the research team of any final changes that may be needed. This will take place at the University of Lincoln and/or via teleconference/Microsoft Teams to suit participants.

SCHEDULE OF PROCEDURES

Informed consent will be taken for each element of the study. Each element will only occur once as follows:

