- Survey on health and social care needs: exact timing is dependent on the stage that probation is at on their roadmap to recovery from the pandemic, but is likely to be over a period of three months between months 3 and 9 of the overall project
- Service user panel: month 7
- Expert panel survey one: month 2
- Systematic review: months 1-8
- Expert panel survey two: months 11-12
- Final discussion of quality indicators: month 16

WITHDRAWAL

Participants can withdraw from any element of the study at any time. For all of the surveys (of service users and the expert panel), data will be collected anonymously. Therefore, participants will be made aware (via the information sheet and consent form) that should they withdraw the data collected to date may not be erased in accordance with the University's Research Privacy Notice and information given in the Participant Information Sheet and may still be used in the final analysis.

ETHICAL AND REGULATORY CONSIDERATIONS

ASSESSMENT AND MANAGEMENT OF RISK

We do not anticipate that taking part in this study will cause any pain, discomfort, or changes to lifestyle for participants. The burden involved will simply be the time to complete a survey/participate in a focus group (service user panel)/complete a survey and rate quality indicators (expert panel). It is possible that reflecting on health needs or past experiences around accessing healthcare may cause distress. Steps have been taken to minimise the burden by keeping the questions asked in each of these elements to a minimum and advising participants that it is up to them what they answer and how they answer – they do not need to share anything too upsetting.

The participant information sheets will make it clear that should someone discuss plans to harm their self/another, or commit a criminal offence, appropriate persons (probation staff) will be aware of this as probation staff will be directly administering the surveys, or giving them out for self-completion, and looking at the participants' answers straight afterwards. Surveys will only be administered in an appropriate space – so if conducted by phone or online (e.g. via Microsoft Teams), a participant will need to have an appropriate (private) space in which to take part.

Page 21 of 25

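### Staff feedback interviews: signed consent is returned through a colleague in probation, so someone in the interviewees' own organisation knows who took part, an avoidable risk to candour in a small qualitative component

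*Protocol*

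**What the plan says.** The Consent section of the protocol has staff interviewees give written consent in this way: "returning the consent form to the member of probation staff inviting people to take part, who will then upload these to a shared file", where the research team can see the forms. Under Sampling, and again under Sampling technique, the protocol says: "An email will be sent via our probation co-applicant to all staff that may have played a role in administering the survey". Recruitment describes the same channel more loosely, with the information sheet and consent form "attached to an email sent to all relevant staff via probation".

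The target, under Size of sample, is small: "We would like 5-10 staff to take part in online/telephone interviews to provide feedback on this". Study Regimen gives the purpose: "to ascertain feedback on what it was like to implement the survey and if/how this could be incorporated into routine practice". The Study Summary adds that the interviews are recorded, transcribed in full and analysed thematically.

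On team membership, the Sampling section states: "A National Probation Service Divisional Director is part of this team". On anonymity, the Withdrawal section says: "For all of the surveys (of service users and the expert panel), data will be collected anonymously". That sentence does not cover the staff interviews. The data protection section does promise, for every part of the research, that responses will be anonymised, reported in aggregate, or both.

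**The concern.** The interviewees are asked to comment on work done within their own organisation: judging who had enough English and capacity, inviting everyone on the caseload, giving reminders and reviewing completed surveys. The most useful answers may be unflattering, for example that the survey was burdensome, that some invitations were missed, or that administration was uneven. If a colleague receives each volunteer's signed form, a member of staff with such things to say may prefer not to come forward, or may say less.

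What is at stake is the staff evidence on whether the survey can be built into routine practice, which bears on the primary objective of better measurement and recording of need. Selection towards the favourable, or a softened account, would be hard to detect afterwards in a thematic analysis of so few interviews.

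**Working it through.** No arithmetic applies. The check sets the relevant sections side by side.

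1. **Who receives the forms.** The Consent section sends them to the member of probation staff who issues the invitation. Sampling says the email goes out via the probation co-applicant. Read together, the recipient is probably the co-applicant, but the protocol does not say so. Either way the recipient is a member of probation staff, and so belongs to the interviewees' organisation.

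2. **Whether there is another route.** Sampling, Sampling technique, Recruitment and Consent describe no way for staff to consent directly to the university. In the text available, the study flowchart box for a volunteer who agrees to be interviewed is incomplete, so nothing is drawn from it.

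3. **What the recipient learns.** The forms show who volunteered. They do not show what was said. With a target of 5-10 interviews, the recipient would hold 5-10 names.

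4. **Whether later safeguards close the gap.** Three provisions bear on this.
   - Data protection: anonymised or aggregate reporting covers all elements, including these interviews. This protects the published account.
   - Withdrawal: anonymous collection is stated for the surveys only.
   - Access to the final dataset: this is given to the research team, which includes a probation Divisional Director. The protocol does not say whether the dataset includes interview transcripts, or whether probation colleagues on the team are kept from identifiable material.

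   A reader who already knows the 5-10 names may be able to attribute an anonymised quotation. Anonymised reporting therefore offsets the risk only in part.

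5. **How other participants consent.** Expert panellists give e-consent inside the online survey. Service user panel members return consent to Revolving Doors Agency, which recruits them. Use of an intermediary is thus not peculiar to the staff interviews. The relevant difference is that the staff intermediary belongs to the organisation whose practice is being discussed.

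6. **What the component feeds.** The stated outcomes are the overview of needs, with the extent to which they are met, and the creation of quality indicators. The interviews give feedback on administration and routine use. They do not enter the weighting, the prevalence estimates, the mixed effects models or the indicator ratings.

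**The case against.** The strongest reply is that the protocol describes an ordinary administrative step. One person collects forms and places them where the researchers can see them. Nothing says that line managers or the wider organisation see the forms, and it is normal for someone on a study team to know who agreed to a recorded interview. The route reveals participation and not content, and reporting is to be anonymised or aggregated. The staff information sheet is not shown and may already give assurances. The proposed change would also leave recruitment by an email sent through probation, so reluctant staff could still stay away.

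Most of this stands and limits the point. It does not remove it: the consent route is written into the protocol, and an assurance in the information sheet would not alter who receives the form.

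A reader might infer more than the documents support:

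- That critical feedback is in fact discouraged. The protocol neither states nor shows this; it is a plausible risk of selection and social-desirability bias.
- That the recipient is the co-applicant, or a senior manager. The recipient is not named, and the protocol does not say whether the Divisional Director is the co-applicant.
- That the organisation as a whole holds a list, or sees what was said. No section says so.
- That the effect can be sized. One critic lost from ten is 1/10 = 10%, and two from five is 2/5 = 40%, but the one or two is an assumption with no source in the documents. A thematic analysis estimates no proportion in any case.

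**Conclusion.** The point holds as a minor, avoidable design weakness. As written, a member of the interviewees' own organisation learns which staff volunteered to comment on the survey's administration and routine use. That creates a risk, not a demonstrated effect, that critical staff will not come forward or will temper their account.

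The conclusion rests on the consent route as stated, on the absence of any direct route in the text available, and on the assumption that some staff would be less candid if a colleague knew they had taken part. The size of the risk cannot be quantified. It is confined to the staff feedback interviews; the prevalence estimates and the quality indicators are unaffected.

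**What to change.** Keep the all-staff email through probation, since it reaches everyone who may have administered the survey. In the Consent section, change the return address so that volunteers send the completed form directly to the university research team, by email or e-consent, and delete the step in which probation staff upload the forms. E-consent is already used elsewhere in the study.

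Add a sentence stating that identifiable interview material (consent forms, recordings and transcripts before anonymisation) is held by the university researchers and is not shared with probation colleagues on the team. Bring the section on access to the final dataset and the staff information sheet into line with this.

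The cost is small: the research team handles the replies itself, and one handling step disappears. If the affected documents already have ethics approval, the protocol's own amendment rules apply. The change reduces volunteer bias but does not remove it, because recruitment would still depend on staff responding to an email sent through probation.
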